Children are enrolled in the study cohort at the age of 6 months, when the program foresees MUAC screening measurements and SQ-LNS distribution by NASG to start. From August 1th, 2021 (start of the program) onwards, NASG in both intervention and comparison study arms are tasked to conduct home visits to pregnant and lactating women and caregivers of children up to 24 months of age to provide BCC on child nutrition, health and WASH. Therefore, it is likely that caregivers with children of 6 months enrolled in the cohort after the start of the program have been exposed to BCC prior to study inclusion. This exposure to BCC may have been greater in the intervention group because in that study group the program formed new NASGs proportionate to village population size (contrary to the comparison group with typically counts 1-2 NASG per village independent of population size). For this reason, all analyses related to study outcomes on the impact pathway related to BCC (knowledge indicators, IYCF, immunization rates, WASH practices, child anthropometry) include the data at enrollment at the age of 6 months. For study outcomes related to activities that only start between the age of 6 and 7 months, like MUAC-based screening and the distribution of SQ-LNS, we consider data related to the program’s impact from the child age of 7 months onwards. To assess the intervention’s impact between study enrollment (child age of 6 months) until the end of the study (9 to 12 months of age)

Treatment of missing data for primary study outcomes

We conducted multiple imputation of missing longitudinal anthropometric data using fully conditional specification, also known as multiple imputation by chained equations which imputes missing values

under the missing at random assumption¹¹. Imputation variables were the wide-form anthropometric measurements and child age, and complete predictors (independent variables) were child sex and randomization stratum. We used 50 imputations with 10 burn-in iterations to allow for convergence to a stationary distribution before the imputation. Imputation quality will be assessed using trace plots by iteration to assess convergence and using box plots to compare distributions of observed and imputed values.

Statistical analysis methods

For the analysis of the longitudinal prevalence of wasting (primary outcome), severe and moderate acute malnutrition and morbidity, the incidence of acute malnutrition and wasting we use mixed-effects Poisson regression models with robust estimation of standard errors to provide adjusted risk estimates. Results from non-adjusted and adjusted regression models will be presented as described under the paragraph on 'Guiding principles and analysis strategy'.

Continuous outcomes (such as WLZ, MUAC, LAZ) that are measured monthly will be regressed over calendar date using a linear mixed-effects model including *health center catchment area* and *child* as a random intercept and *follow-up time* as a random slope. For each model, we assess if the addition of a quadratic term of time improves the model fit significantly by applying a likelihood ratio test comparing the model with and without the quadratic term. To assess the specific impact of the intervention (SQ-LNS, MUAC screening and BCC) from enrollment at the age of 6 months to the end of follow-up, we assess the interaction between intervention allocation and time.

Dichotomous outcomes will be analyzed using linear probability mixed-effects models with robust estimation of the standard errors with *health center catchment area* as random effect and sampling stratum as fixed effect to demonstrate the impact of the intervention on the dichotomous outcome averaged over the follow-up period or at the end of the study. For repeated measures, to assess the specific impact of the intervention (SQ-LNS, MUAC screening and BCC) from enrollment at the age of 6 months to the end of follow-up (cohort 1), we assess the interaction between intervention allocation and follow-up time using a linear probability mixed-effects model with *health center catchment area* and *child* as a random intercepts and *follow-up time* as random slope.

Considerations for analysis

Baseline characteristics

For all variables measured, the available values at enrollment and collected from May to July 2021, i.e. before the start of the intervention, will be considered as baseline characteristics. The background characteristics of subjects who completed the study will be presented by intervention group. Following CONSORT guidelines, no statistical tests will be conducted comparing baseline characteristics between

¹¹ De Silva AP, Moreno-Betancur M, De Livera AM, Lee KJ, Simpson JA. (2017) A comparison of multiple imputation methods for handling missing values in longitudinal data in the presence of a time-varying covariate with a non-linear association with time: A simulation study. *BMC Med Res Methodol*; 17:1–11

study arms. Differences in baseline characteristics will be appreciated by comparing values of means and proportions.

The presentation of baseline characteristics will be done as follows:

- Categorical variables: frequencies and percentages, as appropriate. Percentages will be calculated based on the number of participants for whom data are available.
- Continuous variables: mean and SD or median and interquartile range, as appropriate.

Characteristics	Cohort	Comments/References
Household level		
HH size (mean/SD)	1,3	
Number of under 5 children in household (mean/SD)	1,3	
Number of adults (15-64 y) (mean/SD)	1,3	
Polygamous HH(%)	1,3	
HH food insecurity (mean and proportion of food secure HH)	1,3	Coates J, Swindale A, Bilinsky P. Household Food Insecurity Access Scale (HFIAS) for measurement of food access: indicator guide. Washington, DC: FANTA; 2007. https://doi.org/10.1007/s13398-014-0173-7.2
SES status classification (tertiles, %)	1,3	Principal component analysis will be used to construct a proxy household Socio-Economic Score (SES) using ownership of various assets (an asset is excluded if ownership is below 5% or above 95% on HH level), housing materials, primary source of lighting, primary energy source, and home ownership. Tertiles of the first principal component (i.e., the one with the highest eigenvalue) will be used.
Improved water treatment technologies used (%)	1,3	USAID (2021) Water and development- Indicator handbook. Washington DC
Improved sanitation facility (%)	1,3	USAID (2021) Water and development- Indicator handbook. Washington DC
Handwashing station with soap available (%)	1,3	USAID (2021) Water and development- Indicator handbook. Washington DC
Improved primary water source (%)	1,3	USAID (2021) Water and development- Indicator handbook. Washington DC
Distance to nearest health center, km	1,3	Linear distance between households and the nearest health center calculated using Global Position System coordinates
Distance to nearest Community health worker, km	1,3	Linear distance between households and the nearest Community health worker calculated using Global Position System coordinates. Limited to villages that are covered by a community health worker.
Household head level		
Male head of household (%)	1,3	
Adult (15-64 years) (%)		
Elderly (65+ years) (%)		
Paternal level		
Father is head of HH (%)		
Age (mean/SD)	1,3	
Male (%)	1,3	

Head of household school attendance	1,3	
Has an income generating activity (%)	1,3	
Parental confidence scale	1,3	
Severe clinical range (less than 31)		Črnčec R, Barnett B, Matthey S. Development of an instrument to assess perceived self-efficacy in the parents of infants. Res Nurs Health. Res Nurs Health; 2008
Moderate clinical range (31-35)		
Maternal		
Biological mother (%)		
Age (mean/SD)	1,3	
Spouse of head of household (%)	1,3	
School attendance (Never attended school, %)	1,3	
Has an income generating activity (%)		
Height (meand/SD)	1,3	
Possible depression (EPDS \geq 10)	1,3	Cox JL, Chapman G, Murray D, Jones P. Validation of the Edinburgh postnatal depression scale (EPDS) in non-postnatal women. J Affect Disord. 1996;39:185-9.
Parental confidence scale	1,3	
Severe clinical range (less than 31)		Črnčec R, Barnett B, Matthey S. Development of an instrument to assess perceived self-efficacy in the parents of infants. Res Nurs Health. Res Nurs Health; 2008; 31:442-53.
Moderate clinical range (31-35)		
Number of food groups consumed over last 24h (mean/SD)	1,3	Out of a maximum of 10 food groups as proposed by Martin-Prevel Y, Allemand P, Wiesmann D, Arimond M, Ballard T, Deitchler M, et al. Moving forward on choosing a standard operational indicator of women's dietary diversity. Rome: FAO; 2015. Food groups are starchy staple foods, nuts and seeds, flesh foods, dark green leafy vegetables, pulses, dairy, eggs, vitamin A rich fruits and vegetables, other vegetables and other fruits
Minimum dietary diversity (having consumed at least 5 of 10 food groups during the last 24h)	1,3	Martin-Prevel Y, Allemand P, Wiesmann D, Arimond M, Ballard T, Deitchler M, et al. Moving forward on choosing a standard operational indicator of women's dietary diversity. Rome: FAO; 2015
Body Mass index (kg.m ⁻²) (mean/SD)	1,3	
Underweight (BMI $<$ 18.5) (mean/SD)	1,3	
Assisted delivery of last pregnancy (%)	1,3	
Number of antenatal consultations attended during last pregnancy (%)	1,3	
Breastfeeding, complementary feeding, health and hygiene, MUAC screening, CMAM knowledge score (mean/SD)	1,3	Self-developed questionnaire based on training curricula for GSAN. Mean scores are presented by domain, as well as an overall score based on the 36 questions
Child		
Age (mean/SD)	1,2,3	
Male (%)	1,2,3	

Primiparity	1,3	
Minimum dietary diversity (%)	1,3	Indicators for assessing infant and young child feeding practices: definitions and measurement methods. Geneva: World Health Organization and the United Nations Children's Fund (UNICEF), 2021
Minimum meal frequency(%)	1,3	
Minimum acceptable diet(%)	1,3	
Consumption of iron-rich or iron-fortified foods (%)	1,3	
Hemoglobin concentration (%)	1,3	As measured by hemocue 301
Anemia (hb<7 g/dl)	1,31,3	
Severe anemia (hb<11 g/dl)		
Weight-for-length Z-score (mean/SD)	1,2,3	Relative to WHO 2006 growth reference
Wasting (WLZ<-2 or edema)	1,2,3	Relative to WHO 2006 growth reference
Severe Wasting (WLZ<-3 or edema)	1,2,3	Relative to WHO 2006 growth reference
MUAC (mean/SD)	1,2,3	Relative to WHO 2006 growth reference
Acute malnutrition (WLZ<-2 or MUAC<125mm or edema)	1,2,3	Relative to WHO 2006 growth reference
Severe Acute malnutrition (WLZ<-5 or MUAC<115mm or edema)	1,2,3	Relative to WHO 2006 growth reference
Length-for-age Z-score (mean/SD)	1,2,3	Relative to WHO 2006 growth reference
Stunting (LAZ<-2)	1,2,3	Relative to WHO 2006 growth reference
Weight-for-age Z-score (mean/SD)	1,2,3	Relative to WHO 2006 growth reference
Underweight (WAZ<-2)	1,2,3	Relative to WHO 2006 growth reference
Child development score (DMC-III)	1	Prado, E.L. , Abubakar, A.A. , Abbeddou, S. , Jimenez, E.Y. , Some, J.W. , & Ouedraogo, J.B. (2014). Extending the developmental milestones checklist for use in a different context in Sub-Saharan Africa. Acta Paediatrica , 103,
Gross motor (mean Z-score/SD)	1	Z-scores(individual value minus mean group value divided by the SD) will be calculated using data during the baseline period of the study
Fine motor (mean Z-score/SD)	1	Z-scores(individual value minus mean group value divided by the SD) will be calculated using data during the baseline period of the study
Language (mean Z-score/SD)	1	Z-scores(individual value minus mean group value divided by the SD) will be calculated using data during the baseline period of the study

Effect modification

Studying effect modification of an intervention offers important insights in the mechanism of a possible impact. In this study, we applied a stratified cluster randomized sampling, stratifying by health center catchment area characteristics (urban/rural, proportion of population living >15km from a health center, previous activities on child nutrition delivered by World Vision Mali). To gain more operational insight on how the intervention performed according to stratum characteristics we will assess possible effect modification of the intervention by these strata. Given that these tests are explorative in nature, we assess

interaction terms at a statistical significance set at 10%. Statistical models are the same as described in earlier sections. Results from both adjusted and non-adjusted regression models will be presented. If there are indications of effect modification by stratum characteristics, we will present impact results stratified by stratum.

Sensitivity analyses

We will assess whether impacts on primary outcomes in cohort 1 and 3 are sensitive to the definition of wasting, by assessing impact on wasting prevalence and incidence when wasting is defined with 2 alternative definitions: 1) MUAC < 125 mm or oedema, and 2) WLZ < -2 Z-scores or oedema.

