A population-representative longitudinal study design (**Cohort 1 or Main cohort**) was used enrolling children aged 6 to 6.9 months from May 2021 until November 2021. In addition, a second cohort (**cohort 2 or Treatment cohort**) was constituted consisting of all children admitted to MAM OTP (French: URENAM) and SAM OTP (French: URENAS) provided by first-line health centers and community health workers from May 2021 until February 2022. Finally, study field workers home visited a subsample of children three months after their discharge from SAM or MAM OTP to assess the impact of the intervention on post-treatment relapse rates (**cohort 3 or Relapse prevention study**). While the Main cohort study is an experimental study³, the Treatment cohort and Relapse prevention study are quasi-experimental in nature. The quasi-experimental character of these two sub-studies implies that the random character of the intervention and comparison group is not fully guaranteed. More precisely, children enrolled in the Treatment cohort may not be comparable between study groups because the BCC and SQ-LNS may prevent a proportion of the usual prevalence of wasting. Similarly, a higher screening coverage or screening by family MUAC may refer children with wasting with different characteristics as compared to those in the comparison group. Therefore, any impact or lack of impact of the NASG intervention to support the OTP services needs to be interpreted with caution, as it may be a result of both the intervention and any different characteristics of the enrolled samples of children. For the same reasons, the results of the relapse prevention study must be interpreted bearing in mind possible impacts of the preceding preventive BCC and SQ-LNS and improved screening and referral (studied in the main cohort), as well as possible impacts on the adherence and recovery rates of MAM and SAM OTP (studied in the treatment cohort).

Study outcomes

Primary study outcomes

1. The longitudinal prevalence of wasting in children enrolled at the age of 6 months followed monthly until the age of 12 months or until the end of the study, whatever comes first (**cohort 1 or Main cohort**). This indicator is defined for each child as the number of visits during which nutritional wasting is observed divided by the total number of monthly visits made (by the interviewers).

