2. The recovery rate in children enrolled at the age of 6-23 months for a treatment of up to 3 months in URENAM and URENAS treatment services and followed until their discharge (**cohort 2 or**

³ The main cohort study is an experimental cluster-randomized controlled study that guarantees (if random allocation of clusters is successful) that the samples of children enrolled in the intervention and comparison group have similar household, caregiver, and child characteristics. Therefore, any observed impacts can be exclusively associated with the intervention.

Treatment cohort). This indicator is defined as the number of children declared recovered from wasting according to the criteria of the national program (WLZ-score \geq -1.5 or MUAC \geq 125mm, and absence of bilateral edema during two consecutive visits, within 12 weeks after enrollment in the program) divided by the total number of enrolled children.

3. The prevalence of relapse after URENAS or URENAM treatment defined as the proportion of children (9-18 months of age) with WLZ-score <-2 or MUAC <125 mm or bilateral pitting edema three months after discharge from SAM or MAM OTP (**cohort 3 or Relapse Prevention study**).

Secondary study outcomes

For Cohort 1

- The longitudinal prevalence of:
 - o MAM defined as the number of MAM diagnoses divided by the total number of monthly visits made by the survey teams.
 - o SAM defined by the number of SAM diagnoses divided by the total number of monthly visits made.
- The incidence of:
 - o Wasting defined as the number of new cases of wasting diagnosed during the monthly visits made by the survey teams.
 - o MAM defined as the number of new MAM cases diagnosed during the monthly visits made by the survey teams.
 - o SAM defined as the number of new SAM cases diagnosed during the monthly visits made by the survey teams.
- The prevalence of anemia and severe anemia defined as the proportion of children with a hemoglobin level below 11g/dL and 7 g/dL respectively, at age of 12 months or at the end of the study.
- The mean hemoglobin concentration at age of 12 months or until or at the end of the study.
- The prevalence of stunting defined as the proportion of children with LAZ <-2 (according to the 2006 WHO reference) at age of 12 months or at the end of the study.

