For each stratum, the president of FELASCOM drew a piece of paper (containing the name of a health center catchment area) from the bag and drew also one of the envelopes (containing the unique two-letter code). As he unfolded the piece of paper, he read aloud the name of the health center catchment area and showed the name of written on the piece of paper to all participants and wrote that name on the front of the envelope. This process continued until all 46 envelopes were linked to a health center catchment area. After this step, the IFPRI principal investigator projected the two-letter codes with study arm assignment to all participants. During this last step, the envelopes were opened one by one and the president of the FELASCOM read the name of the health center catchment area and the two-letter code aloud so that the result could be written by the secretary on a flip chart and made visible to all participants.

Sample Size

Sample sizes were calculated prior to randomization and data collection. However, as mentioned earlier, 3 study clusters were omitted from the study during the baseline survey because of severe security threats. In addition, the sponsor allowed the study to be extended by two months to the end of February 2022. We therefore recalculated the sample size for each of the primary outcomes for 42 study clusters instead of the original 45 and including two additional months of recruitment of study subjects.

Cohort 1 - Main Outcome: Longitudinal prevalence of wasting

Scenario with 45 clusters available (SAP version 1.0)

Considering a baseline longitudinal prevalence of 13.2% (obtained from the control group of the PROMIS Mali study) with a standard deviation (SD) of 0.239 for the control group and an SD of 0.189 for the treatment group, a mean cluster size of 35 (anticipating a loss of follow-up of 15%), a statistical power of 80%, a type I error of 5% and an intra-cluster coefficient of 0.04, we need at least 44 clusters to detect a minimum difference of ~ 4.84 percentage points in the 6-14 months age group.

Scenario with 42 clusters available (SAP version 2.0)

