where C_{in} = current wasting, SAM or MAM cases in SAM or MAM OTP, C_{out} = current wasting, SAM or MAM cases not in SAM or MAM OTP, R_{in} = recovering wasting, SAM or MAM cases in SAM or MAM OTP, and R_{out} = recovering wasting, SAM or MAM cases not SAM or MAM OTP estimated for World Vision screening campaigns as $\frac{1}{k} \times (R_{in} \times \frac{C_{in} + C_{out}}{C_{in}} - R_{in})$ and k = the mean length of a recovered episode of wasting, assumed to be 5.1 months for MAM and 5.7 months for SAM based on a previous longitudinal study conducted in an adjacent region¹⁰. For single coverage estimate using the Main cohort data, R_{out} is estimated by observing recovery between two monthly measurements.

Data management

The management of all research data will follow IFPRI's institutional research data management protocol, overseen by the IFPRI Data Governance Committee, as well as UNICEF data governance standards. All received data will be carefully anonymized and de-identified so that the privacy of participants and research subjects is fully protected. Personally Identifiable Information data (PII; names, telephone numbers, GPS coordinates, date of birth) will be stripped from the research data when receiving the data on the server. During data collection, PII data will be stored in a separate secured server folder accessible only to the Principal Investigators. PII data will only be used to identify a household to conduct additional verification of previously collected data. When data collection and data validation have been completed, PII data will be destroyed.

In accordance with IFPRI's policy on research data management and open access, at the time of publication of scientific articles presenting the primary results, fully anonymized databases will become a public good and will therefore be made available to the scientific community, government, partners.

All data collection is scheduled to start once the study trial is registered on clinicaltrials.gov.

Statistical analysis

Data sources

The training of NASG groups is scheduled to be concluded in the last week of July 2021. Therefore, cohort 1 and 2 data from May to July 2021 will be used to assess the study baseline and to inspect imbalances in sample characteristics between study arms. Follow-up data from August 2021 to February 2022 will be

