⁹ Balegamire S, Siling K, Alvarez JL, Guevarra E, Woodhead S, Norris A. 2015. "A Single Coverage Estimator for Use in SQUEAC, SLEAC, and Other CMAM Coverage Assessments." *Field Exchange*, vol. 49

¹⁰ Barba, Francisco M., Lieven Huybrechts, and Jef L. Leroy. 2020. "Incidence Correction Factors for Moderate and Severe Acute Child Malnutrition From 2 Longitudinal Cohorts in Mali and Burkina Faso." *American Journal of Epidemiology* 189(12): 1623–27

used to assess the impact of the program. For cohort 3, data from October 2021 to February 2022 will be used to study the impact of the intervention on relapse.

Guiding principles and analysis strategy

Data will be analyzed on intent-to-treat basis. To allow for an analysis “as randomized” in the presence of missing data, we will impute missing data of the primary outcomes of the longitudinal study using a multiple imputation strategy under the *missing at random* assumption. Data management, data cleaning, and statistical analyses will be done using Stata 17.0 (Statacorp, USA). The statistical significance will be set at 5%. All statistical tests will be two-sided. The analysis of primary study outcomes will not be adjusted for multiple testing (n=3 primary study outcomes) given the data involved represent three distinct experimental and control study arms with each one primary study outcome.

We present results from non-adjusted and adjusted linear mixed effects regression models. The non-adjusted models use *health center catchment area* as a random intercept and sampling stratum as a fixed effect to represent the study design. Adjusted regression models further include as fixed effects the cluster baseline means (May-July 2021 period) of the outcome under analysis, month of enrollment into the study (cohort effect), child sex, child age, and primiparity. Furthermore, if any baseline household, caregiver or child characteristic is imbalanced (absolute difference of ~5pp) between study groups, we conduct an additional robustness analysis adjusting the analysis for this covariate.

Cohort 1 specific considerations

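### Several time windows for primary outcomes 2 and 3 cannot be applied as written: relapse visits fall outside their window, the May–July baseline mean fails for both, and the recovery cut-off is unstated

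*SAP*

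**What the plan says.** **Recovery (cohort 2).** Under Primary study outcomes, item 2, children are enrolled for up to three months of treatment in "URENAM and URENAS treatment services and followed until their discharge". The numerator is recovery "within 12 weeks after enrollment in the program) divided by the total number of enrolled children". Study design defines the cohort as all children admitted to treatment "provided by first-line health centers and community health workers from May 2021 until February 2022". The Sample Size section says that "the sponsor allowed the study to be extended by two months to the end of February 2022" and recalculates "including two additional months of recruitment of study subjects".

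**Analysis periods.** Under Statistical analysis, Data sources: "cohort 1 and 2 data from May to July 2021 will be used to assess the study baseline". Then: "Follow-up data from August 2021 to February 2022 will be" used to assess impact. For cohort 3 the impact data are those of October 2021 to February 2022.

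**Relapse (cohort 3).** The sampling section takes children discharged as recovered between May and December 2021 and visits them three months later. Eligibility requires at least three months since recovery.

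**Adjusted models.** Guiding principles and analysis strategy adds to every adjusted model "the cluster baseline means (May-July 2021 period) of the outcome under analysis". It exempts neither cohort 2 nor cohort 3. Cohort 1 specific considerations puts the start of the program at 1 August 2021.

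**The concern.** Outcomes 2 and 3 each need about three months of observation after a child enters the risk set (12 weeks from admission, three months from discharge). The periods in Data sources do not say whether they refer to admission, visit or discharge date, and for some children the required time does not fit inside the period.

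Three things are at stake:

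- **Outcome 3.** Part of the sampled cohort cannot contribute inside the stated window, and one prespecified covariate cannot be computed.
- **Outcome 2, adjusted model.** The baseline mean may contain outcomes that the intervention can already affect.
- **Outcome 2, numerator.** If data really close in February 2022, a child admitted in January who recovers in time in March stays in the denominator as a failure. The recovery rate would then partly measure speed of recovery and favour the faster arm. Speed could differ, because Table 1 gives the intervention arm home visits during treatment.

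**Working it through.** **(a) Relapse calendar.** Discharge month plus three months, using the dates in the cohort 3 sampling section and Data sources:

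- May → August, June → September: before the October–February window opens.
- July → October, August → November, September → December, October → January, November → February: inside it (5 of 8 months).
- December → March 2022: after the window and after the end of the study.

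The earliest possible visit is August 2021 (a May discharge). A May–July 2021 cluster mean of relapse therefore cannot exist. Data sources itself names only cohorts 1 and 2 as sources of baseline data.

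**(b) Baseline mean of recovery.** 12 weeks = 84 days.

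- 31 July 2021 − 84 days = 8 May 2021. Only admissions of 1–8 May complete the window by 31 July.
- May–July has 31 + 30 + 31 = 92 days, and 92 − 8 = 84 of them (84/92 = 91.3%) do not complete.
- If the period sorts by admission date, the mean includes recoveries on or after 1 August, under the program.
- If outcomes close on 31 July, the mean is cut short by the same rule in both arms before the program starts. It is a noisier covariate but not a biased one.

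**(c) Impact window for recovery.**

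- 28 February 2022 − 84 days = 6 December 2021, the last admission with a full window.
- 1 August to 28 February = 31 + 30 + 31 + 30 + 31 + 31 + 28 = 212 days. 7 December to 28 February = 25 + 31 + 28 = 84 days. 84/212 = 39.6%.
- 28 February 2022 + 84 days = 23 May 2022, the date by which every admission has had 12 weeks.

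Many children recover before week 12, so 39.6% counts admission days, not lost outcomes. As an illustration only, assume even admissions, data closed on 28 February and recovery t days after admission. The share wrongly scored as failures is then 0.79 × t/212: 10.4% at 28 days and 20.9% at 56 days. A one-week difference in speed with equal true recovery gives 0.79 × 7/212 = 2.6 points. The SAP gives no recovery times.

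**(d) Cost of restricting admissions.** Inputs from Sample Size, cohort 2, version 2.0: 42 clusters (21 per arm), 50 children each, 79% recovery, ICC 0.05, 80% power, two-sided 5%.

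- *The plan's own figure.* Design effect 1 + 49 × 0.05 = 3.45; effective n per arm 21 × 50/3.45 = 304.3. The detectable increase is 8.43 points (unpooled normal formula) or 8.76 with a continuity correction. The stated ~9.0 is reproduced to rounding.
- *Power at 50 per cluster, 79% vs 88%.* SE = √[(0.79 × 0.21 + 0.88 × 0.12)/304.3] = √(0.2715/304.3) = 0.0299; 0.09/0.0299 − 1.96 = 1.05; power 85.4%.
- *Restricted to 1 August–6 December.* 212 − 84 = 128 days; 50 × 128/212 = 30.2 per cluster, taking the 50 as August–February admissions. With 30: design effect 2.45, effective n 257.1, SE 0.0325, z = 0.81, power 79.1%, detectable difference 9.09 points.

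**The case against.** The strongest reply concerns (c). Cohort 2 is defined by admission, its primary outcome follows children to discharge, and its secondary outcomes (treatment duration, weight gain, MUAC gain) run from admission to discharge in the total sample. The data come from registers, which can be copied after the last admission without visiting families. Version 2.0 is dated 22 September 2022, well after 23 May 2022. On that reading, the August–February period sorts children by admission date and no outcome is lost. This is the more natural reading, and much of the reply stands. What remains is that no section states it, while Data sources, read literally, ends the impact data in February.

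A reader might therefore infer that the recovery comparison is biased as planned, that 40% of outcomes are lost, or that power collapses. The SAP does not support any of these. Each needs a February data close, open cases scored as failures, and recovery times that the SAP does not give.

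On (b), the baseline mean enters only the adjusted model, a non-adjusted model is also reported, and a mean truncated at 31 July does not bias the comparison. That stands. Under admission-date sorting, however, which is the reading that rescues (c), the mean does include recoveries under the program.

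On (a), a sampling frame may be wider than an analysis window, and May–June discharges precede the program, so leaving them out can be defended. Neither argument places the December discharges or supplies a baseline relapse mean.

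**Conclusion.** The point holds as a should-fix inconsistency of windows. Three parts need no assumption beyond the SAP's own dates:

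- December discharges cannot have their relapse visit inside the October–February window, and May–June discharges reach three months before it opens.
- The prespecified baseline mean does not exist for relapse.
- For recovery, that mean is incomplete for 84 of 92 admission days or includes recoveries under the program.

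The fourth part is conditional. If outcomes closed in February 2022, admissions after 6 December 2021 (39.6% of impact-period admission days) lack a full window, and the error favours the faster-recovering arm. If registers were read to completion, this problem is absent. The illustrative percentages for misscored children and for a one-week speed difference show the direction and mechanism; the severity does not rest on them.

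**What to change.** 1. **Outcome 3.** Make the discharge and analysis windows agree, and say where May–June and December discharges belong. Drop the May–July mean for relapse, or replace it with a measure that exists before 1 August. This is a wording change, unless visits already made have to be reassigned.
2. **Outcome 2 covariate.** Replace the May–July recovery mean with a cluster measure fully observed before 1 August, for example mean WLZ or MUAC at admission in May–July, or omit it. No new data are needed, since nutritional status at enrollment is already a cohort 2 outcome.
3. **Outcome 2 window.** State that the periods classify children by admission date and that register outcomes are taken to 23 May 2022. Given the date of version 2.0, the extraction date should be known. If the outcomes were collected, this costs one sentence and keeps the planned 50 per cluster.
4. **If they were not collected,** base the primary recovery analysis on admissions from 1 August to 6 December 2021. With even admissions this leaves about 30 of 50 children per cluster, a detectable difference of about 9.1 points (against the stated ~9.0) and about 79% power for 79% versus 88% (85% with 50).
5. A 12-week cumulative recovery estimate that keeps all admissions, censors open cases and treats default, death and transfer as competing events should be at most a sensitivity analysis, because it replaces the stated proportion of all enrolled children.
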